3.3.2 Overall Survival

To overall survival (OS) after lung SBRT for up to 30 months after SBRT.

Endpoints: Overall survival after lung SBRT (every 6 months for the first year, then annually).

3.3.3 Correlation between Lymphocyte Depletion and Function and Radiation Dosimetry

Identify correlations between lymphocyte depletion and functional impairment with dose to great vessels, lung tissue, heart, and other normal tissue containing large amounts of circulating blood.

Endpoints:

- 1. Dose to circulating blood
- TLC and functionality of T cell sub types.

3.3.4 Optimization of Predictive Algorithm

Improve our existing simulation algorithm to predict the total lymphocyte loss for a given RT beam plan using the clinical trial data.

Endpoints: This model will take into account patient specific (i) total blood volume, (ii) initial lymphocyte count, (iii) tumor volume, (iv) the organs from the Thorax CT data set, and (v) time dependent dose map through each organ for a given delivery system. These data will be combined with general information from published literature such as (i) varying blood output to organs (ii) blood velocity for all organs (iii) random mixing of blood after each trip through the exposed dose area, with the remaining blood volume of the body.

3.3.5 Description of Changes in Lymphocyte Subtypes

Describe the changes in lymphocyte subtypes following SBRT in Arms A and B

Endpoint: Quantity of lymphocyte subtypes (e.g. CD4, CD8) prior to and 4 weeks following SBRT

4. PATIENT SELECTION

[figure not shown]

Figure 2: Definition of proximal bronchial tree, for the distinction of centrally located tumors from peripheral tumors (taken from Radiation Therapy Oncology Group (RTOG) 0915 protocol).

4.1 Eligibility

4.1.1 Inclusion Criteria

- 1. Willingness and ability to provide written informed consent and to comply with the study protocol.
- Diagnosis of biopsy confirmed non-small cell lung cancer (NSCLC) with planned treatment with SBRT as definitive therapy OR imaging confirmed lung lesion for which SBRT is planned for primary lung cancer (when clinician determines biopsy is not indicated), Registration should occur within 5 business days (before or after) of planning CT.
- 3. Patients must decline surgery or tumor(s) must be considered to be medically inoperable
- 4. Location and size of tumor- Participants must have either:
 - peripherally located tumors (> 2 cm in all directions from the proximal bronchial tree; see Figure 2 above) as defined by RTOG 0915, OR
 - centrally located tumors (tumor size ≤ 5 cm, tumors within or touching the zone of the proximal bronchial tree or adjacent to mediastinal or pericardial pleura) as defined by RTOG 0813.

- 5. Patients with recurrence of prior surgically treated lung cancers are eligible if no further surgery is planned and they otherwise meet the eligibility criteria.
- 6. Measurable disease on chest CT, PET CT, CT simulation at diagnosis (must be within 8 weeks of SBRT).
- 7. Pre- radiation therapy total lymphocyte count > 0.5k/μL on blood count drawn within 2 weeks prior to registration.
- 8. In the opinion of the treating clinician, patient is medically able to tolerate the study SBRT treatment of 50-60 Gy in 5 fractions.
- 9. ECOG performance status of 0-2.
- 10. Age ≥ 18 years.
- 11. If participant is a woman of childbearing potential (WOCBP), agreement to adhere to contraception requirements from the time of consent through completion of SBRT (see section 4.1.3).

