Assess if the lymphodepletion predictive algorithm developed by UVA coupled with the existing optimization algorithm in radiation treatment planning software predicts the magnitude of lymphocyte depletion in a prospective cohort of patients treated with lung SBRT.	After randomization and completion of treatment planning, the algorithm will predict the decrease in lymphocyte count for each participant (in Arms A and B) at 4 weeks after SBRT. The endpoints are:

	a) the within patient difference in the change from baseline in predicted and observed lymphocyte counts b) the within patient difference in the percent change from baseline in predicted and observed lymphocyte counts
Determine if lymphocyte-sparing SBRT planning (Arm A, investigational) results in less in vivo lymphocyte depletion compared to controls who receive standard SBRT planning (Arm B, control).	Observed changes in lymphocyte count from baseline and 4 weeks after completion of lung SBRT for participants in each arm. Expected lymphocyte nadir time point of 4 weeks following SBRT will be used to estimate both the actual and percentage decreases in lymphocyte counts seen in each arm.
Secondary	
Describe the adverse event profile of participants treated with and without lymphocyte-sparing SBRT planning (Arms A and B).	Frequency, severity, and duration of adverse events according to CTCAE version 5.0
Determine if our lymphodepletion predictive algorithm coupled with the existing optimization algorithm in radiation treatment planning software predicts the magnitude and trajectory of lymphocyte depletion in a prospective cohort of patients treated with lung SBRT.	After randomization and completion of treatment planning, the algorithm will predict the decrease in lymphocyte count for each participant (in Arms A and B) for each follow-up time point (at end of SBRT, and 4 weeks and 6 months after SBRT). The predicted time course of lymphocyte count will be compared with both the actual and percentage decrease in lymphocyte count observed.

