3.1.2 Impact of Lymphocyte-Sparing SBRT Planning Objectives on Post-SBRT Lymphocyte Count

Determine if lymphocyte-sparing SBRT planning (Arm A, investigational) results in less *in vivo* lymphocyte depletion compared to controls who receive standard SBRT planning (Arm B, control).

Hypothesis: We hypothesize that we can generate treatment plans that both meet standard of care objectives for organs-at-risk (OAR) and result in a smaller reduction in lymphocyte count by reducing exposure of circulating lymphocytes in great vessels.

Endpoint: Observed changes in lymphocyte count from baseline and 4 weeks after completion of lung SBRT for participants in each arm. Expected lymphocyte nadir time point of 4 weeks following SBRT will be used to assess changes in lymphocyte counts in each arm.

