5. STATISTICAL CONSIDERATIONS

Study populations Any participant who initiates either standard or optimized SBRT will be considered evaluable for adverse events. Participants with observed changes in lymphocyte counts at any of the follow-up times will be considered evaluable for the analyses of changes in lymphocyte counts.

Randomization and stratification

[figure not shown]
Participants will be randomized to standard or optimized SBRT in a 1:1 ratio using randomly permuted blocks. Block sizes of 2 or 4 will be randomly chosen with equal probability. The randomization will be stratified by central or peripheral lung lesion (section 4.1.1)

Sample size and power The first aim is to compare the actual and predicted values from the simulations. We will calculate the empirical distribution function of the difference between predicted and actual, both in terms of lymphocyte counts and percent change from pretreatment counts. Current simulation is able to predict to 17% accuracy, with a standard deviation of 15%. The model will be considered an improvement if 80% of the predictions are within 10% of the actual counts or percent changes. With a sample of size 50 evaluable, the one-sample t-test has 95% power, with a one-sided significance level of 5%, for testing whether the mean percent difference is less than 17%, when the true mean is 10%.

The second aim is to compare standard versus optimized SBRT on the basis of the primary outcome, lymphocyte drop at 4 weeks. The sample size was chosen to have sufficient power for comparing the groups using a repeated measures model for comparing the groups. Estimates of effect sizes and variation were based on repeated measures models, with change points at 4 and 12 weeks, fit to retrospective data on lymphocyte drop within 24 weeks following standard SBRT. A spatial-power model was used for the covariance matrix of percentage changes from baseline in lymphocyte counts,

yielding an estimated standard deviation of 10.5 percentage points and a within-subjects correlation estimate of 0.40 for observations taken 1 week apart. The fitted model, overlaid on the individual patient profiles is displayed above.

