6. REGISTRATION PROCEDURES

Participants cannot be registered until institutional IRB approval of the protocol and consent are obtained. Registration and randomization should occur around the time of planning CT (+/- 5 business days). SBRT must begin within 4 weeks after registration/randomization.

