8.2 Research Blood

Research blood will be collected according to the study calendar of assessments in *section 9*. 40 ml of blood will be collected at two time points (pre SBRT and 1 month after SBRT) in green top tubes. Following collection, the blood will be transported at room temperature to [name] laboratory for processing and analysis.

Blood will be analyzed in [name] lab. Research tubes will be labeled directly with a unique identifier ID and associated with the UVA IRB HSR number. All leftover research blood will be stored in [name] lab at UVA once analysis described in the sections below is completed.

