9. STUDY CALENDAR OF ASSESSMENTS

Procedures	Screening/Baseline ¹	SBRT (5 clinic days)	Completion of SBRT ⁵	4 weeks +/-2 weeks following SBRT	3 months +/-2 weeks following SBRT	6 to 9 months following SBRT	Overall Survival (every 6 months for one year and then annually, by phone or medical record review)
Informed consent	X						
Demographics	Х						
Medical history	Х						
Randomization	X^7						
Concomitant medication review	X8		X			X	
Physical exam	Х		Х		Х		
COVID-19 Questions	Х		Х		Х	Χ	
Vital signs	Х		Х		Х		
Height	X (last recorded for standard clinical care)						
Weight	Х		X ⁶			X ⁶	
Performance status	X		X			Х	
Serum or urine pregnancy test (Women of Childbearing Potential Only)	Х						
0 110 1 1 (00)							
Overall Survival (OS)							Х
Hematology- CBC with Diff	X		X ⁴	Х		Х	X ³
Research Blood	X ²			Х			
Planning/Chest CT	X (w/in 8						
scan with contrast	wks of SBRT) ⁷				X ⁶		
Review of Medical Record (see section 8.1.4)	Х		Х		Х	Х	Х
Adverse event review and evaluation	X					X	
SBRT		Х					

¹ All screening procedures should occur up to 1 month prior to registration unless otherwise specified

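### The only scheduled pre-SBRT lymphocyte count can be up to 6 weeks old at the first fraction and baseline is not otherwise dated, so real pre-treatment change would be scored as algorithm error in Aim 1

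*Combined protocol and SAP*

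**What the plan says.** Criterion 7 in Section 4.1.1 requires a lymphocyte count above 0.5k/μL "on blood count drawn within 2 weeks prior to registration". Section 6.1 has eligibility settled before registration, so this count precedes registration. Section 6 then states that "SBRT must begin within 4 weeks after registration/randomization".

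In the Section 9 calendar, the row "Hematology- CBC with Diff" has one entry before SBRT, under Screening/Baseline and without a footnote. The next is at completion of SBRT. Footnote 1 gives the general rule: "All screening procedures should occur up to 1 month prior to registration unless otherwise specified". Criterion 7 is such a specification, so 2 weeks governs the lymphocyte count.

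A second pre-SBRT draw is planned. Section 8.2 says "40 ml of blood will be collected at two time points (pre SBRT and 1 month after SBRT) in green top tubes", and calendar footnote 2 places the first of these after registration and before SBRT. No CBC is attached to it.

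Both primary endpoints are changes from baseline. For Aim 1, the synopsis lists "the within patient difference in the change from baseline in predicted and observed lymphocyte counts", with a percent-change version. For Aim 2, Section 3.1.2 gives "Observed changes in lymphocyte count from baseline and 4 weeks after completion of lung SBRT for participants in each arm". Section 5 says lymphocyte counts will be quantified at baseline and later. It neither dates the baseline draw nor says which count to use if there are several.

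**The concern.** A change-from-baseline endpoint attributes to treatment everything that happens between the two draws. If the first draw is weeks before treatment, an infection or a course of steroids in the gap is counted as part of the SBRT effect. The protocol accepts that counts respond to such events. Section 8.1.3 asks that steroids and immune modulators be avoided around blood draws, and the summary of changes explains that COVID questions were added because infections and vaccines could affect counts.

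The exposure is greatest in Aim 1. That endpoint is a within-patient difference between prediction and observation, taken over both arms, so nothing subtracts out a change that occurred before the first fraction. The success rule is tight (80% of predictions within 10%), and a sound algorithm could be marked down for change it was never meant to predict. The per-arm decreases that the synopsis also calls for would carry the same component.

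**Working it through.** **Age of the baseline count.** Inputs: 2 weeks (criterion 7) and 4 weeks (Section 6). Maximum age at the first fraction = 2 + 4 = 6 weeks. SBRT takes 5 to 10 business days (Section 7.1.4), or 1 to 2 weeks, and the primary draw is at 4 ± 2 weeks (Section 9). Baseline to primary draw can therefore span 6 + 2 + 6 = 14 weeks, against 2 + 6 = 8 weeks with a count at the first fraction.

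**The plan's own Aim 1 figure.** Section 5 states "Current simulation is able to predict to 17% accuracy, with a standard deviation of 15" percent, and 95% power for a mean of 10% against 17%, n = 50, one-sided 5%. Noncentrality = (17 − 10)/15 × √50 = 3.30. Power is 94.6% with the noncentral t and 95.1% with the normal approximation, so the stated figure is reproduced.

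**How drift enters.** In points of percent change, observed change = SBRT effect + drift.
- Aim 1: prediction error = algorithm error + drift. Nothing cancels.
- Aim 2: with mean drift m in both arms, each arm's mean change moves by m and the A-minus-B contrast moves by m − m = 0.

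**Illustration for Aim 1.** The documents give no drift size, so every drift value here is an assumption.

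*80%-within-10% rule*, with a perfect algorithm and normal, unbiased drift of SD s. The share within 10 points is 2Φ(10/s) − 1:

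| Drift SD (points) | Share within 10 |
|---|---|
| 5 | 95% |
| 7.8 | 80% |
| 10 | 68% |

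*t-test*, if drift adds m points to the mean error, with noncentrality (7 − m)/15 × √50:

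| m (points) | Power |
|---|---|
| 0 | 94.6% |
| 1 | 87.4% |
| 2 | 75.2% |
| 3 | 58.5% |
| 5 | 23.7% |

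**Does a fresher baseline reduce random variance?** Section 5 gives an SD of 10.5 points and a correlation of 0.40 at 1 week under a spatial-power model. Those were estimated on percent changes after SBRT; applying them to the counts is an assumption. SD of a difference at lag t weeks = 10.5 × √(2(1 − 0.40^t)).
- Count at the first fraction to the nominal 4-week draw, 5 to 6 weeks: correlation 0.40^5 = 0.010 to 0.40^6 = 0.004, SD 14.8.
- Count 6 weeks old to the same draw, 11 to 12 weeks: correlation essentially 0, SD 14.8.

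Under that stationary model the variance of the change score hardly moves. What a fresher baseline removes is real change before treatment, not ordinary fluctuation.

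**The case against.** The strongest reply is that the plan never says the eligibility count is the analysis baseline. The Screening/Baseline column also holds a draw made after registration, and nothing forbids a repeat CBC. That is correct: the link is inferred from the single calendar entry. But a site that follows the calendar would have only that count, and the missing definition itself needs repair.

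A reader might infer that Aim 2 is biased too. The documents do not support this. The count precedes randomisation, so drift is equal in expectation across arms and drops out of the comparison. Bias would need a different time from registration to SBRT by arm. Planning follows randomisation and Arm A has extra optimisation, so a difference is possible, but the documents contain no evidence of one. Nor can a loss of Aim 2 precision be claimed by adding drift variance to the 10.5 points: that is already an SD of changes from baseline, so the addition may double count.

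It can also be said that baseline age would not decide the 80% rule. If the stated 15% SD is read as unbiased normal prediction error, 2Φ(10/15) − 1 = 50% of predictions fall within 10% with no drift. With an added drift SD of 10 the combined SD is √(15² + 10²) = 18.0 and the share is 42%. This stands: the perfect-algorithm figures show how sensitive the rule is and do not forecast the result.

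The plan does limit some sources of drift. It discourages steroids near draws, records medications from 28 days before registration, and excludes recent systemic therapy and major surgery. These measures reduce drift without dating the baseline.

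A reader might also combine the general 1-month screening window with the 4 weeks to SBRT and reach more than 8 weeks. Criterion 7 sets the shorter window for this count, so 6 weeks is the limit.

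**Conclusion.** The point holds for Aim 1 and for the per-arm decreases from baseline. As written, the plan permits a baseline lymphocyte count up to 6 weeks old at the first fraction and gives no other dated definition. Real change in that interval would be charged to the algorithm and would be included in each arm's reported decrease. It does not undermine the randomised Aim 2 contrast, short of an arm difference in time to SBRT that nothing in the documents shows.

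The size cannot be fixed from the documents. Six weeks is a ceiling, drift is not quantified, and the figures for the 80% rule and the t-test are conditional on assumed drift. The conclusion also assumes that the single calendar CBC is the analysis baseline. The case for acting is that the defect is plain, bears on a primary endpoint and is cheap to remove.

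**What to change.** - **Section 9:** attach a CBC with differential to the research draw already scheduled after registration and before SBRT, and give that draw a window close to the first fraction. The window is needed because the research draw may itself fall up to 4 weeks before treatment. The calendar already holds the end-of-SBRT count to within 3 days, so a window of that order looks workable; its length is the sponsor's choice.
- **Section 5:** define baseline, for all change-from-baseline and algorithm analyses, as the last count before the first fraction. Reference predicted and observed changes to that same count, and keep the earlier count for eligibility only.
- **Reporting:** tabulate the interval from baseline count to first fraction by arm, so that any arm difference in time to SBRT is visible.

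A side benefit concerns the exploratory subset endpoint (Section 3.3.5). A count from the same draw would allow baseline CD4 and CD8 fractions to be expressed as absolute quantities, although the documents do not say that this is how the quantities will be derived.

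Cost: one extra CBC tube per patient at a scheduled venepuncture and a few lines of text. No extra visit is needed, though the research draw loses some scheduling freedom.

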4.1.2 Exclusion Criteria

- 1. Prior history of radiation therapy within 2 years of registration, however radiation therapy for skin cancer is allowed
- 2. Systemic anti-cancer therapy within the last year prior to registration or planned use during or within 6 months post SBRT follow up timeframe (see study calendar).
- 3. Major surgery within the last 30 days before registration and/or planned before the completion of the 6 months post SBRT follow up timeframe (see study calendar).
- 4. Subject is a prisoner.
- 5. Subject is a pregnant woman.
- 6. Subject is not medically able to tolerate the study SBRT treatment of 50-60 Gy in 5 fractions or cannot comply with other aspects of the study including serial bloodwork.
- 7. Subject has HIV, AIDS, any type of hepatitis and/or any blood borne infectious disease for which the research lab cannot receive blood samples.

4.1.3 Contraception Requirements

Women of childbearing potential must agree to use adequate contraception prior to study entry and through completion of SBRT.

Women of childbearing potential (WOCBP) includes any female who has experienced menarche and who has not undergone successful surgical sterilization (hysterectomy, bilateral tubal ligation or bilateral oophorectomy) or is not postmenopausal [defined as amenorrhea ≥ 12 consecutive months]; or women on hormone replacement therapy (HRT) with documented serum follicle stimulating hormone (FSH) level > 35 mIU/mL

[1] Prior to study enrollment, WOCBP must be advised of the importance of avoiding pregnancy during trial participation and the potential risk factors for an unintentional pregnancy

19

- [2] The following birth control methods are allowed during the study:
 - a. Barrier methods:
 - [1] Intra-uterine device (IUD)
 - [2] Diaphragm with spermicide

- [3] Cervical cap with spermicide
- [4] Condom with spermicide
- b. Abstinence (no heterosexual activity)

[figure not shown]
5. STATISTICAL CONSIDERATIONS

Study populations Any participant who initiates either standard or optimized SBRT will be considered evaluable for adverse events. Participants with observed changes in lymphocyte counts at any of the follow-up times will be considered evaluable for the analyses of changes in lymphocyte counts.

Randomization and stratification

[figure not shown]
Participants will be randomized to standard or optimized SBRT in a 1:1 ratio using randomly permuted blocks. Block sizes of 2 or 4 will be randomly chosen with equal probability. The randomization will be stratified by central or peripheral lung lesion (section 4.1.1)

Sample size and power The first aim is to compare the actual and predicted values from the simulations. We will calculate the empirical distribution function of the difference between predicted and actual, both in terms of lymphocyte counts and percent change from pretreatment counts. Current simulation is able to predict to 17% accuracy, with a standard deviation of 15%. The model will be considered an improvement if 80% of the predictions are within 10% of the actual counts or percent changes. With a sample of size 50 evaluable, the one-sample t-test has 95% power, with a one-sided significance level of 5%, for testing whether the mean percent difference is less than 17%, when the true mean is 10%.

The second aim is to compare standard versus optimized SBRT on the basis of the primary outcome, lymphocyte drop at 4 weeks. The sample size was chosen to have sufficient power for comparing the groups using a repeated measures model for comparing the groups. Estimates of effect sizes and variation were based on repeated measures models, with change points at 4 and 12 weeks, fit to retrospective data on lymphocyte drop within 24 weeks following standard SBRT. A spatial-power model was used for the covariance matrix of percentage changes from baseline in lymphocyte counts,

yielding an estimated standard deviation of 10.5 percentage points and a within-subjects correlation estimate of 0.40 for observations taken 1 week apart. The fitted model, overlaid on the individual patient profiles is displayed above.

With n=25 patients, measured at baseline and 4 and 24 weeks months post radiation, the F-test in the repeated measures model provides 80% power for comparing the mean lymphocyte depletion profile over the follow-up period between the groups. For the power calculation, we assumed that in the optimized dose participants. mean lymphocytes relative to baseline are equal to Δ + $(1-\Delta)\mu(t)$, where $\mu(t)$ is the mean estimated from historical controls at time t = 0, 4, or 24 weeks. With this, $\Delta = 0$ means no effect of the optimization; $\Delta = 1$ means no

lymphocyte depletion with optimized SBRT treatment. *Figure 3* displays the mean profile for Δ = 0.60, a profile for which n = 25 per group yields 80% power for the F-test, with a 2-sided significance level of 5%. For the specific comparison at 4 weeks, a contrast in the repeated measures model has more than 99% power for the assumed profile. We computed power for the comparing the entire trajectory, and not just at 4 weeks, because of the uncertainty in the point at which the maximum drop and the maximum difference between the groups will occur. To allow for 10% dropout, 55 patients will be enrolled in the study.

Analyses. For the first aim, which compares the actual and predicted lymphocyte counts, the empirical distribution function of the differences, both in terms of the lymphocyte count and the percentage change from baseline, will be tabulated. We will assess the proportion of cases in which the predicted values is within 10% of the actual value. In addition to computing the empirical distribution functions, exploratory analyses will assess patient characteristics associated with the magnitude of the deviation between predicted and actual values.

For the second aim, repeated measures models will be used to compare the groups with respect to the percentage drop in lymphocyte counts. The stratification factor will be used as a covariate in the model. Contrasts will be used to compare the groups at specific time points, including the 4 week post-treatment time point, where we anticipate there will be the greatest difference between the standard and optimized SBRT groups. The sample size was based on an assumed spatial power covariance structure, but we will consider other covariance matrices as well, such as random effects models. In exploratory analyses will tabulate local control as well as adverse events (see *section 8*) and estimate differences these between groups. Kaplan–Meier curves will be used to summarize overall survival in each of the standard and optimized SBRT groups.

Quantitative analysis of blood counts and radiation dose to the great vessels

We will collect blood, serum and PBMC at baseline and at end of treatment, weeks 4, and 24 after treatment for all study patients. The reference point for post-treatment blood collection will be the start date of radiation therapy to permit intergroup comparisons between the two study arms. This comparison framework was selected based on our available preliminary data, which

suggests that RT-induced lymphocyte effects occur as early as one week following radiation initiation due to the high radiosensitivity of circulating lymphocytes. We will quantify absolute neutrophils, hemoglobin, platelet, and lymphocyte counts for all patients at these time points and compare the changes between the groups and also compare the lymphocyte count results to what was predicted by the simulation algorithm. We will perform a multivariate analysis to identify the correlation between TRL and mean/integral radiation dose to the great vessels. Since substantial circulating blood is also present in the heart and lungs we will also correlate mean heart and lung dose with TRL. Measurement of the magnitude of lymphocyte depletion and correlation with great vessel, lung, and heart integral dose will be performed and compared to the predicted levels for the simulation algorithm.

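### Aim 1's only powered test, a mean error below 17%, does not show that dose-based prediction works if the error is in percentage points, and the plan does not state the scale

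*Combined protocol and SAP*

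**What the plan says.** All of the figures are in Section 5 (Statistical Considerations) unless noted.

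- Reference performance: "Current simulation is able to predict to 17% accuracy, with a standard deviation of 15" percent.
- Powered test: "With a sample of size 50 evaluable, the one-sample t-test has 95% power, with a one-sided significance level of 5" percent, "for testing whether the mean percent difference is less than 17%, when the true mean is 10" percent.
- Success rule: "The model will be considered an improvement if 80% of the predictions are within 10% of the actual counts or percent changes".
- Analyses paragraph: "We will assess the proportion of cases in which the predicted values is within 10% of the actual value". The empirical distribution of the differences is also tabulated. Neither the t-test nor the 80% threshold is repeated there.
- Endpoint (Synopsis, Table 1), in its percentage form: "the within patient difference in the percent change from baseline in predicted and observed lymphocyte counts". The other form uses counts.
- Spread of the outcome, from the second aim's sample-size text: "yielding an estimated standard deviation of 10.5 percentage points", for percentage change from baseline, from a model "fit to retrospective data on lymphocyte drop within 24 weeks following standard SBRT".

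The documents do not say whether 17% is signed or absolute. Nor do they say whether it is in percentage points, relative to the observed count, or relative to the observed change. Aim 1 has no no-dose comparator, calibration slope or correlation of observed on predicted change.

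**The concern.** The first primary objective is to show that an algorithm driven by radiation dose to blood predicts each patient's lymphocyte loss. An error threshold supports that claim only if a forecast without dose information would usually miss it. Here the reference error of 17 is larger than the outcome's own spread of 10.5, so quoting the average drop might pass the test as easily as a good dose model. Section 2 states that the algorithm is ultimately meant to guide dose optimization during planning. A pass that does not separate it from the average would be a poor basis for that step.

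**Working it through.** **Inputs.** From Section 5: null 17, alternative 10, SD 15, n = 50, one-sided 5%; outcome SD 10.5 points; Δ = 0.60; 4-week contrast with over 99% power at 25 per arm. The mean 4-week drop on standard SBRT appears only in a figure that is not shown, so it is varied. Errors are taken as normal.

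**1. The plan's own figure.** Noncentrality = (17 − 10)/15 × √50 = 3.30, df 49, one-sided 0.05. Power is 94.6% (95.1% by the normal approximation). The stated 95% reproduces.

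**2. No-dose forecast, standard arm, percentage points.** Every participant is given the historical mean change, so the error is N(0, 10.5).
- Mean absolute error = 10.5 × √(2/π) = 8.4.
- SD of the absolute error = 10.5 × √(1 − 2/π) = 6.3.

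**3. Both arms.** The history is standard SBRT only, so the forecast is off by the arm difference d in Arm A. There the mean absolute error is that of |N(d, 10.5)|. The pooled value averages the two arms. On the normal approximation, 99% power for the 4-week contrast needs d of about 10.5 × √(2/25) × (1.96 + 2.326) = 12.7; 12.9 is used. Under Δ = 0.60 the control drop is d/0.60. Power is simulated with 25 per arm.

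| d (points) | Control drop | Arm A error | Pooled error | SD of pooled absolute error | Power to reject 17 |
|---|---|---|---|---|---|
| 0 | – | 8.4 | 8.4 | 6.3 | about 100% |
| 12.9 | 21.5 | 14.0 | 11.2 | 8.3 | 99.9% |
| 18 | 30 | 18.4 | 13.4 | 9.7 | 85% |
| 24 | 40 | 24.1 | 16.2 | 11.6 | 7% |
| 30 | 50 | 30.0 | 19.2 | 13.9 | under 5% |

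**4. Other readings of the 17%.**
- Signed differences: any unbiased constant has mean 0 and passes. The historical mean at d = 12.9 has a mean signed error of 12.9/2 = 6.5 in size, also below 17.
- Relative to the observed count: the pooled mean error of the historical-mean forecast is 9.7, 12.3, 16.2, 21.2 and 27.5% for control drops of 10, 20, 30, 40 and 50 points. It is below 17% only up to a drop of about 30.
- Relative to the observed change: its pooled median error is 43% to 63%, so it does not beat 17%.

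**5. Do the stated figures fit together?** If 17 and 15 are the mean and SD of absolute error in points, the root mean square error is √(17² + 15²) = 22.7, and 22.7/10.5 = 2.2 times the outcome SD.

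**6. The 80%-within-10% rule.**
- No-dose forecast, standard arm: 2Φ(10/10.5) − 1 = 65.9% within 10 points; chance of at least 40 of 50 is 2.2%. Pooled at d = 12.9: 52%, chance under 0.01%.
- An algorithm that reaches the powered target of 10 with normal errors has error SD 10/√(2/π) = 12.5. It puts 2Φ(10/12.5) − 1, about 58%, within 10, with under 0.1% chance of 40 of 50. Meeting 80% needs an error SD of 7.8 or less.
- A skewed (gamma) absolute error with mean 10 and the stated SD of 15 gives 69%, still short of 80%.

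**The case against.** The strongest reply is the 80% rule. It is the only text that says when the model counts as improved, and its 10% margin is the one carried into the Analyses paragraph. A no-dose forecast misses it on every reading tried. That stands. A reader might infer that Aim 1 as a whole can be passed without dose information, and the documents do not support this: the weakness lies in the 17% test.

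A reader might also infer that the no-dose forecast beats the 10% target as well as the 17% reference. It does so in the standard arm (8.4). Aim 1 covers both arms, however, and pooled the figure is 11.2 at a 12.9-point arm difference.

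The result also depends on an unstated scale and an unknown arm difference. That is correct, and it limits the claim.

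Dose is examined elsewhere: Section 3.3.3 and the end of Section 5 plan correlations of depletion with great-vessel, heart and lung dose, and Aim 2 randomizes the planning method. Those analyses relate dose to depletion. They do not ask whether the algorithm's predictions improve on the average.

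Finally, the 80% rule and the powered target are not logically incompatible. If 80% of absolute errors were 2.5 and 20% were 40, the mean would be 10, the SD 15, and the rule met. The plan does not assume such a distribution, and it offers no power for the rule. This is also a pilot, which argues for a clear report more than for a harder hypothesis test.

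**Conclusion.** The concern holds for the 17% t-test, which is the only powered Aim 1 criterion. It assumes absolute error in percentage points, normal errors, the retrospective SD of 10.5 and a historical mean that carries over to the trial's standard arm. A no-dose forecast then rejects 17% with about 99.9% power at a 12.9-point arm difference, 85% at 18 and 7% at 24. If the error is relative to the count or to the change, the result may not hold. If differences are signed, any unbiased constant passes.

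Two further problems remain. The 17/15 pair does not sit with 10.5 points: either the scales differ, or the current algorithm predicts worse than the mean. A reader might conclude the latter, but the documents do not settle it. And the two success criteria can give opposite answers, with no statement of which governs, whether it applies to counts or percent changes, or what power the 80% rule has. It would be too strong to say that the benchmarks carry no information, because the 80% rule does discriminate.

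**What to change.** In Section 5:

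1. State the scale of the 17% and 15%, state that differences are absolute, and reconcile both figures with the 10.5-point SD.
2. State which criterion governs the Aim 1 conclusion, and whether on counts or on percent change, and give its power.
3. Report alongside it the algorithm's 4-week mean absolute error against a no-dose comparator: the retrospective mean change, already fitted, applied to each participant's baseline. Give a confidence interval for the paired difference, by arm and pooled.
4. Report the calibration slope and the correlation of observed on predicted change.

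The cost is SAP wording and a little more analysis on data already collected, with possibly a less favourable claim. The paired comparison need not replace the stated success rule. As a one-sided 5% test at n = 50 it would have roughly 78% to 85% power if the algorithm explains 40% to 45% of the variance, but about 44% if it explains 20%. An estimate with an interval is therefore enough for a pilot.
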